9.1. Confidentiality of the data

The data of the patients will be collected anonymously from the moment of signing the informed consent. To do this, a representative code of the patient will be created, which will include the initials of the study, followed by a hyphen and the inclusion number. The clinical documentation of the patient and the tube containing the blood of the patients or control subjects will contain only this information. The informed consent will be kept in a different location from the clinical information and under lock and key.

The transcriptomics data will remain anonymized and will receive the name designated at the time of inclusion in the study. The data will be deposited and protected on outsourced servers in compliance with the European regulations of the General Data Protection Regulation (GDPR). AWS is currently used to safeguard the information.

9.2. Data quality assurance and control

a. Data entry and storage

electronic platform [RedCap](#). This electronic data capture platform is covered by security systems, in compliance with current regulations on data protection. The access control will

be configured in such a way that there are two owners with the project administrator role, who will be in charge of authorizing the access of the study personnel, as necessary, and with access levels according to the roles and responsibilities. The electronic forms that will be used for data upload will be specifically designed for this study. The data will be entered by the researcher at the recruitment center, via the web. The data will be stored on a central outsourced server (AWS).

b. Data quality control monitoring

Data storage and processing will be centralized in xx. The personnel in charge of entering the data will be trained in the use of RedCap for this purpose.

The following quality controls will be carried out:

- Validation rules generated according to the nature of the variables, programmed through the data validation modules available in RedCap.
- Automatic query generation (queries) according to pre-established validation rules, to be answered by researchers on the sites.
- Manual design of explanatory queries, to be answered by the researchers on the sites.
- Registration system, history and query control (queries).
- Periodic reports on the status of data entry, query generation and response, on a weekly basis.

c. Elaboration of the manual of procedures

A manual of procedures will be developed where the procedures for the implementation of the baseline data collection questionnaire, blood extraction and follow-up will be described.

d. Training and certification

In order to participate in the study, all staff must attend a training session prior to the start of fieldwork. Training sessions will include all aspects of the protocol and procedures manual regarding enrollment, follow-up, protocol, and measurement

procedures. Those who have acquired the expected skills will be certified to carry out the study procedures. Staff will be retrained if necessary.

e. Site Monitoring Visits and Audits

Monitoring visits and audits will be conducted at the health centre in order to follow up on the progress of the fieldwork, identify problems and carry out retraining if necessary.

9.3. Calculation of the sample size

The calculation of the number of patients to demonstrate a positive effect for the use of peripheral blood transcriptomics for the diagnosis of the presence of severe coronary calcification is carried out based on previous experiences by the group of researchers. There is still no standardized methodology in the medical literature to perform the sample calculation of this type of analysis, since it is very recent and is in the exploration phase. Studies *silico* carried out by this group of researchers and the preliminary clinical studies carried out previously, it was observed that at least a sample of 800 patients is necessary for a robust training of the artificial intelligence algorithm that detects transcriptional differences between patients with or without a solid tumor. (for example, breast tumor). Therefore, 800 patients will be included based on the minimum number necessary to perform an adequate training of an artificial intelligence algorithm.

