5.1. In silico developments

In our laboratory, we have developed a methodology for transcriptome analysis based on extensive bioinformatic processing of a biological sample and its subsequent interpretation employing a *deep learning algorithm*. In this way, we can incorporate all the genes read in a sequence and perform a classification using a supervised method. This algorithm has proven robust and highly accurate in our preliminary tests. The development comprises a *pipeline* that takes the RNA-seq sample in its crudest state and analyses it entirely, including coding and non-coding RNAs, circular RNAs and the blood microbiome. The algorithm is trained with all the samples of a cohort, previously classified, and later, the algorithm is validated with 10 or 20% of the samples.

The analysis of the efficiency of the algorithm was performed with different RNA-seq databases available in digital repositories. First, we used the GTEx database, which has taken *postmortem* from dozens of people and performed sequencing of them. In total, 30 different tissues containing 11,866 sequences were analyzed. The analysis of our algorithm achieved a correct prediction in 99.1% of the cases (figure 1). The few errors correspond to potentially similar tissues (for example, breast with fatty tissue).

Subsequently, we analyzed the Genomic Data Commons (GDC) database, which has RNA sequencing of biopsies from different tumors. We analyzed 10,000 biopsies distributed in 34 tumors. Again, the predictive capacity of the algorithm was very high, reaching 97.5% (figure 2). These two analyses show that the algorithm has a great classification capacity between multiple samples.

We then performed a sensitivity analysis of the algorithm. To do this, we started with 100 random samples taken from brain tumors from the GDC database, 50 of them corresponding to GBM and 50 of them to GL. With them, new training was carried out in which we achieved a precision of 100%, which translates into an area under the curve (ROC) of 1. Successively, we removed samples at random, performing effective training with only 30 samples (15 of each group). Therefore, the algorithm has a very efficient behaviour with a low number of clinical cases. This reflects the fundamental differences in gene expression between the two groups of tumors.

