5.2. Preliminary studies

We previously developed a clinical protocol with the aim of perfecting the methodology that will be used in this study. The initial goal was to develop blood collection, RNA isolation, library generation for sequencing, and RNA sequencing. Briefly, the preliminary results of these steps, performed on 540 samples from 3 different studies, are described below.

First, a robust methodology was established to obtain an RNA sample from peripheral whole blood (without cell separation). Samples were collected in PaxGene RNA tubes through antecubital vein puncture. No adverse effects were observed in this procedure. Samples were stored at -20°C until RNA extraction. This step was performed through the use of a specific kit (Thermo-Fischer). As a result, it was possible to consistently obtain RNA samples in sufficient quantities for sequencing in all cases. Then, the library was built, a process in which the RNA is transformed into cDNA (complementary DNA), from which the RNA corresponding to ribosomes and globin are extracted, fragmented, and finally the adapters are added at the ends. Again, the library construction was developed in a robust way for all the analyzed samples.

Subsequently, RNA sequencing was performed at a depth of 100 million reads. Between 20 and 25 thousand genes expressed in peripheral blood were detected in all the samples (n=540). In a series of patients, computed tomography was performed to determine the degree of calcification of the coronary arteries (Coronary Calcium Score, CCS). An analysis of gene expression in peripheral blood was performed and genes related to the degree of coronary calcification were found.

[figure not shown]

Figure 3: Preliminary results. We analyzed 38 samples from patients who had coronary calcium measured. The left panel shows the result of a PCA analysis where a moderate but significant reduction in dimensionality is found based on the extent of coronary calcium. The heatmap shows the differentially expressed genes between the two groups.

6. Study Objectives

Primary Objective

The primary objective of the study is to evaluate the diagnostic accuracy of peripheral whole blood transcriptomes analyzed by an artificial intelligence algorithm to detect the presence and extent of coronary calcification in individuals without a history of known cardiovascular disease.

Specific Primary Objectives

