1. To classify transcriptomes according to the presence and extent of coronary calcification by noncontrast cardiac CT.
2. Train artificial intelligence algorithms with information from the transcriptome to recognize the presence and extent of calcification in coronary arteries.

-
3. To determine the degree of diagnostic accuracy of the method to detect the presence and extent of coronary calcification non-invasively.

Secondary objectives

1. To determine the degree of diagnostic accuracy of the method to detect the presence and extent of:
 - Aortic
 - calcification Aortic valve calcification
 - Hepatic steatosis
 - Volume of epicardial fat
 - Volume of high-density epicardial fat (upper quartile)
 - Enlargement of cardiac cavities To
2. To explore differences in transcriptomics of peripheral blood between patients who did and did not develop a CV event during follow-up.
3. To explore different electrocardiographic patterns according to the results of cardiac CT and peripheral blood transcriptomics.
4. Generate a polygenic risk score (PRS) from the transcriptome and/or exome sequencing and associate it with the transcriptome and coronary calcification.

7. Methods

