8.5. Analysis of cardiac CT

The presence of CAC and its extension will be evaluated using both ordinal variables (number of segments with CAC and number of affected vessels, and qualitatively: absence, mild, moderate, and severe; and the number of coronary segments with calcification) as continuous variables (Agatston units). The presence and extension of calcifications at the level of the aortic valve and the thoracic aorta (Agatston units) will also be evaluated independently. The extent of aortic calcification will be evaluated in sections that include from the bifurcation of the pulmonary artery as the upper limit to the diaphragm as the lower limit.

Quantitative analysis of SCC will be performed using dedicated software (HeartBeat-CS, Philips Healthcare, Best, The Netherlands). Finally, the volume and density of epicardial fat will be calculated by evaluating the volume of tissue with a density between -190 and -30 HU located in the area between the epicardium and the pericardium, the bifurcation of the pulmonary artery as the upper limit, and the diaphragm as lower limit.

Finally, the density of the hepatic parenchyma will be calculated through a region of interest >100 mm² at the level of the right and splenic lobes. From these measurements, the presence of hepatic steatosis will be defined from a quotient of less than 1.

At least 20% of the participants (randomly selected) will have a double reading of the main outcome of the study (presence or extent of CACs). This reading will be carried out by an expert external to the group of researchers of the study and blind to the first reading. In case of disagreement, consensus will be sought between the two experts. The aim of this process is to enhance the internal validity of the study.

The epicardial fat volume analysis will be performed by experts from the University of Palermo (Italy).

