9.4. Analysis plan

For the description of the general characteristics of the study population, descriptive statistics such as means, medians and proportions will be used. To calculate the diagnostic performance of the method, the following will be calculated:

- True Positives (TP) or the probability that the test is positive since the disease is present

-
- True Negatives (TN) or the probability that the test is negative since the disease is not present.
 - False Positives (FP) or Type I Error
 - False Negatives (FN) or Type II Error
 - Sensitivity: $VP/VP+FN$
 - Specificity: $VN/ VN+FP$
 - Precision or accuracy: $VP/VP+FP$ or sensitivity + (1-specificity)

The diagnostic precision can vary between 0.5 and 1, where 1 represents a perfect diagnostic value and 0.5 is a test without diagnostic discriminatory capacity. An area under the curve (AUC) will also be performed to determine the diagnostic capacity of the trained algorithm.

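### The primary accuracy target is not defined: section 6 asks for presence and extent of calcification, 9.3 argues from severe calcification and a solid-tumour classifier, and 9.4 gives no cut-off, confidence interval or extent analysis

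*Combined protocol and SAP*

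**What the plan says.** **Objective.** The primary objective in section 6 is to evaluate the diagnostic accuracy of the method "to detect the presence and extent of coronary calcification in individuals without a history of known cardiovascular disease". Specific primary objective 3 repeats it: "To determine the degree of diagnostic accuracy of the method to detect the presence and extent of coronary calcification non-invasively".

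**Reference standard.** Section 8.5 records calcification on several scales, including "qualitatively: absence, mild, moderate, and severe; and the number of coronary segments with calcification) as continuous variables (Agatston units". No Agatston boundary is given for any of the four grades.

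**Sample size.** Section 9.3 describes a calculation "for the diagnosis of the presence of severe coronary calcification is carried out based on previous experiences" of the research group. It then says that at least 800 patients are needed for robust training of an algorithm that "detects transcriptional differences between patients with or without a solid tumor. (for example, breast tumor".

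**Analysis.** Section 9.4 lists true and false positives and negatives, sensitivity, specificity and a precision or accuracy measure. The first is worded "True Positives (TP) or the probability that the test is positive since the disease is present". It adds: "An area under the curve (AUC) will also be performed to determine the diagnostic capacity of the trained algorithm". It does not say which calcification level counts as disease, gives no confidence interval, and says nothing about grades or Agatston units.

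**Evaluation set.** Neither 9.3 nor 9.4 says how many patients will be scored out of sample. Section 5.1, describing the existing pipeline, says "the algorithm is validated with 10 or 20% of the samples".

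**The concern.** Sensitivity, specificity and AUC cannot be computed until someone decides which patients are diseased. Sections 6, 9.3 and 9.4 point to three different things: presence and extent, severe calcification, and an unnamed disease. As written, the cut-off could be chosen after the results are seen.

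Extent is half of the primary objective. It is measured carefully in 8.5, but 9.4 states no analysis of it.

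The number 800 rests on a rationale for another disease. The section mentions earlier experience, in silico work and preliminary clinical studies, but gives no calcification prevalence, expected accuracy or interval width. The only calcification data described are the 38 samples in 5.2, and neither the text nor the figure caption reports an accuracy for them.

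**Working it through.** **1. Can 800 be reproduced?** No. The documents give no prevalence, expected sensitivity, specificity or AUC, interval width, error rate or power, so no formula can be run from their own inputs. 800 can be neither reproduced nor refuted.

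**2. The target, section by section.**

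| Section | Target | Cut-off |
|---|---|---|
| 6 | Presence and extent | None |
| 8.5 | Four grades; Agatston units; segment and vessel counts | None |
| 9.3 | Presence of severe calcification; then solid tumour | None |
| 9.4 | An unnamed disease, two classes | None |

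**3. How much the choice of target matters.** Every input except N = 800 is assumed: AUC A = 0.75; prevalence of any calcification 40-60%; prevalence of severe calcification 5-10%; all 800 patients scored by a model not trained on them and treated as independent. Hanley-McNeil, with n1 diseased and n0 not diseased:

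Var = [A(1-A) + (n1-1)(Q1-A²) + (n0-1)(Q2-A²)] / (n1·n0)

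Here Q1 = A/(2-A) = 0.600, Q2 = 2A²/(1+A) = 0.6429 and A² = 0.5625. For severe at 10% (n1 = 80, n0 = 720):

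Var = (0.1875 + 79×0.0375 + 719×0.0804)/57,600 = 0.00106, SE = 0.0325, and 1.96×SE = 0.064.

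| Target | Prevalence | Cases of 800 | 95% half-width |
|---|---|---|---|
| Any | 60% | 480 | 0.033 |
| Any | 50% | 400 | 0.034 |
| Any | 40% | 320 | 0.036 |
| Severe | 10% | 80 | 0.064 |
| Severe | 5% | 40 | 0.089 |

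The severe interval is 1.8 to 2.7 times as wide as the interval for any calcification (0.0637/0.0356 = 1.79; 0.0890/0.0331 = 2.69).

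**4. Which measures would show extent?** Take a predictor that detects presence with AUC A but carries no information on extent among calcified patients. Assume A = 0.75-0.80, a share p0 = 40-60% with zero Agatston, and 10% severe.

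- *All-patient Spearman with Agatston* (mid-ranks for the zeros): 6·p0(1-p0)(A-0.5)/√(1-p0³). At p0 = 0.4, A = 0.75: 6×0.24×0.25/√0.936 = 0.37. At p0 = 0.6, A = 0.80: 6×0.24×0.30/√0.784 = 0.49.
- *AUC, severe versus everyone else*: 0.5 + [p0/0.90](A-0.5). At p0 = 0.4, A = 0.75: 0.5 + 0.444×0.25 = 0.61. At p0 = 0.6, A = 0.80: 0.5 + 0.667×0.30 = 0.70.
- *Four-grade quadratic-weighted kappa*: about 0.30-0.42 by simulation, with the score cut at the observed grade shares and mild to moderate at 1:1 or 2:1.
- *Restricted to calcified patients*: Spearman is about 0, and the AUC for severe versus other calcified patients is about 0.50.

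The first three measures therefore look encouraging for a test that knows nothing about extent. The restricted measures do not.

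**The case against.** Several objections deserve weight.

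- *9.4 could already cover extent.* Its two-class measures could be applied at each boundary between the four grades, and 5.1 reports multi-class use of the pipeline. So a reader who infers that these statistics cannot address extent goes too far. What stands is that no boundary is stated, no such use is planned, and a split that pools non-calcified with calcified patients is raised by presence alone.
- *The study is exploratory.* Section 9.3 says the field is in an exploration phase with no standard method for sizing training. That is a fair reason not to give a power calculation. It does not prevent naming the target or stating an expected interval width, and section 6 makes diagnostic accuracy the primary objective.
- *The evaluation set.* A reader might infer from 5.1 that only 80 or 160 patients will be tested, with much wider intervals. The documents do not support this. The share describes the existing pipeline, and the same sentence first says training uses the whole cohort, so it does not establish a hold-out. Precision for 80 or 160 patients is hypothetical; what stands is that the number is unstated.
- *Choice of extent statistic.* Insisting on a rank correlation would be a preference. A severe-versus-other-calcified AUC removes the presence signal equally well and uses a statistic already in 9.4. A calcified-only interval that excludes no association is also a low bar: with 320-480 calcified patients, a Spearman of about 1.96/√319 = 0.11 to 1.96/√479 = 0.09 would pass. That shows association with extent, not diagnostic accuracy.

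**Conclusion.** The point holds and should be fixed before the analysis. The primary accuracy result has no defined target, graded extent has no stated estimate, no confidence intervals are planned, and the rationale for 800 belongs to a different disease.

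A reader might infer that 800 is too small. The documents do not show that: adequacy depends on prevalence, expected accuracy and the number scored out of sample, and none of these is given. The supported conclusion is that 800 is not justified for this question.

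The size of the effect (0.033-0.036 against 0.064-0.089) is an illustration. It rests on assumed prevalences, an AUC of 0.75 and valid out-of-sample scoring of all 800. The inconsistency between sections 6, 9.3 and 9.4 rests on the text alone and needs none of these assumptions.

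**What to change.** (a) **Target.** Name one primary two-class target, with an Agatston cut-off chosen by the sponsor, in the same words in 6, 9.3 and 9.4. Report sensitivity, specificity and AUC with 95% confidence intervals on patients not used to train the model that scores them, and state how many that is.

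(b) **Sample size text.** In 9.3, remove the solid-tumour rationale and give the expected half-width for that target over a stated prevalence range. Keep 800.

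(c) **Extent.** State the grade cut-offs in 8.5. Add to 9.4 an extent analysis with 95% confidence intervals that includes at least one measure restricted to patients with Agatston above zero, for example the AUC for severe versus other calcified patients, or Spearman with the Agatston score. Use a network output trained on grade or extent, so that a null result tests the objective. Show the 4×4 grade table. Do not treat an all-patient correlation, a weighted kappa alone or a severe-versus-rest AUC alone as evidence for extent. Report the size of the calcified-only estimate, not only whether its interval excludes no association.

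**Cost.** Wording in four sections and a little more analysis of data already collected. A network trained only on presence would not serve for (c), so an output trained on grade or extent may be needed. Scoring all 800 out of fold means training the network several times, and the intervals must respect the folds. The stated precision will look weaker, especially for severe calcification and for extent, where only calcified patients count.

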9.4. Analysis plan

For the description of the general characteristics of the study population, descriptive statistics such as means, medians and proportions will be used. To calculate the diagnostic performance of the method, the following will be calculated:

- True Positives (TP) or the probability that the test is positive since the disease is present

-
- True Negatives (TN) or the probability that the test is negative since the disease is not present.
 - False Positives (FP) or Type I Error
 - False Negatives (FN) or Type II Error
 - Sensitivity: $VP/VP+FN$
 - Specificity: $VN/ VN+FP$
 - Precision or accuracy: $VP/VP+FP$ or sensitivity + (1-specificity)

The diagnostic precision can vary between 0.5 and 1, where 1 represents a perfect diagnostic value and 0.5 is a test without diagnostic discriminatory capacity. An area under the curve (AUC) will also be performed to determine the diagnostic capacity of the trained algorithm.

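### Section 9.4 gives two non-equivalent formulas for precision or accuracy; neither is accuracy, and one scores a perfect test and a coin flip alike

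*Combined protocol and SAP*

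**What the plan says.** Section 9.4 (Analysis plan) lists the quantities to be calculated for diagnostic performance. The relevant line is "Precision or accuracy: $VP/VP+FP$ or sensitivity + (1-specificity"), with two names and two expressions, each pair joined by 'or'. The next sentence sets a scale: "The diagnostic precision can vary between 0.5 and 1, where 1 represents a perfect diagnostic value and 0.5 is a test without diagnostic discriminatory capacity". The AUC is listed as a further measure: "An area under the curve (AUC) will also be performed to determine the diagnostic capacity of the trained algorithm".

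The same list describes the cells of the two-by-two table as probabilities, not counts: "True Positives (TP) or the probability that the test is positive since the disease is present" and "False Positives (FP) or Type I Error". Sensitivity and specificity are given as "Sensitivity: $VP/VP+FN" and "Specificity: $VN/ VN+FP". VP and VN are evidently untranslated abbreviations for TP and TN, and brackets are missing from all three ratios. I supply the brackets and do not count either feature as an error.

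No other section gives a formula for accuracy. Diagnostic accuracy is the subject of the primary objective, of the third specific primary objective and of the first secondary objective (section 6).

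**The concern.** A single measure should have a single formula, and the formula should match its name. Here the two expressions are offered as interchangeable although they measure different things. The second rises as specificity falls, so it rewards false positives.

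An analyst who follows the line could report PPV, or this sum, under the name accuracy. Some wrong values would be noticed because they fall outside the stated 0.5-to-1 scale. Others would fall inside it and pass as plausible. An analyst who sees the problem would still have to choose the intended measure, possibly after seeing the results.

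**Working it through.** **Inputs.** The expressions and the 0.5-to-1 scale come from section 9.4, and N = 800 from sections 7.1 and 9.3. The documents give no prevalence, so I assume 30% and show 10% and 50% where it matters. The example sensitivities and specificities are also assumed.

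**Formulas compared**
- Accuracy = (TP+TN)/(TP+TN+FP+FN)
- First expression, from counts: TP/(TP+FP), which is PPV at the study prevalence
- First expression, from rates (TP = sensitivity, FP = 1 − specificity): sens/(sens + 1 − spec), which is PPV at 50% prevalence
- Second expression: sens + (1 − spec)
- Balanced accuracy = (sens + spec)/2

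**Step 1: try to reproduce the plan's own scale (perfect = 1, uninformative = 0.5).**

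Second expression, which needs no prevalence:
- perfect: 1 + 0 = 1.00
- coin flip: 0.5 + 0.5 = 1.00
- sensitivity and specificity both 0.90: 0.90 + 0.10 = 1.00; both 0.60: 0.60 + 0.40 = 1.00
- always positive: 1 + 1 = 2.00; always negative: 0 + 0 = 0.00
- uninformative at 0.20/0.80: 0.20 + 0.20 = 0.40; at 0.80/0.20: 0.80 + 0.80 = 1.60

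The range is 0 to 2, and the scale is not reproduced.

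First expression from counts: a perfect test scores 1, but a coin flip scores the prevalence, which is 0.10, 0.30 and 0.50 at 10%, 30% and 50%. The scale is reproduced only at 50%.

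First expression from rates: perfect 1/(1+0) = 1; coin flip 0.5/(0.5+0.5) = 0.5 at every prevalence. These two anchors are reproduced, though the ratio is undefined for an always-negative test.

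Balanced accuracy: perfect 1; coin flip, always positive and always negative all 0.5. The scale is reproduced, but 9.4 does not give this formula.

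**Step 2: is either expression accuracy?** With 800 patients at 30% prevalence there are 240 with and 560 without the condition.

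| Test (sens/spec) | TP | FN | TN | FP | Accuracy | PPV, counts | Ratio, rates | Sum |
|---|---|---|---|---|---|---|---|---|
| A (0.90/0.50) | 216 | 24 | 280 | 280 | 496/800 = 0.62 | 216/496 = 0.44 | 0.90/1.40 = 0.64 | 1.40 |
| B (0.70/0.95) | 168 | 72 | 532 | 28 | 700/800 = 0.875 | 168/196 = 0.86 | 0.70/0.75 = 0.93 | 0.75 |
| C (0.10/1.00) | 24 | 216 | 560 | 0 | 584/800 = 0.73 | 24/24 = 1.00 | 0.10/0.10 = 1.00 | 0.10 |

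Tests A and B show that the sum can reverse the ranking given by accuracy. For this pair the reversal does not depend on the 30%: accuracy of A against B is 0.54 against 0.925 at 10% prevalence and 0.70 against 0.825 at 50%, while the sum stays at 1.40 against 0.75. A's 1.40 would be seen to be off the stated scale; B's 0.75 would not.

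Test C shows that the first expression is not accuracy under either reading. It scores a perfect 1.00 while missing 216 of 240 cases; accuracy is 0.73 and balanced accuracy (0.10 + 1.00)/2 = 0.55.

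**The case against.** The strongest reply is that a numerator has been lost. If TP and FP are rates, as 9.4 words them, the denominator of the first expression is exactly sensitivity + (1 − specificity). The second expression would then be the first with its numerator missing, and the intended form would be sens/(sens + 1 − spec), which gives the plan's 1 and 0.5 for a perfect and an uninformative test. The rate reading also leaves the sensitivity and specificity lines correct, because the true-positive and false-negative rates sum to 1, as do the true-negative and false-positive rates. The missing brackets and mixed abbreviations make a translation or typesetting loss believable.

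This is plausible but cannot be shown from the text. It does mean that only the sum, and the first expression read as counts, conflict with the 0.5-to-1 sentence; the first expression read as rates does not. It does not rescue the definition, because the restored ratio is PPV at 50% prevalence and not accuracy, as test C shows.

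It can also be said that the practical effect is small. Accuracy and PPV can both be recomputed from the same table, and the example tests were chosen to illustrate. Section 5.1 reports the proportion classified correctly and links 100% precision to a ROC area of 1, which suggests the team knows the usual measures. Those points limit the severity, but they do not supply the missing formula.

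**Conclusion.** The line is wrong as written. The two expressions are not equivalent and neither is accuracy. The values of 1.0 for both a perfect test and a coin flip, and 2.0 for an always-positive test, follow from algebra alone. The accuracy and count-based PPV figures rest on assumed prevalences and on illustrative sensitivities and specificities.

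The scope is this one measure. Sensitivity, specificity and the separately planned AUC are unaffected, no measure is designated primary, and nothing in the sample size or any decision rule uses the line. It should still be corrected, because it is the plan's only definition of accuracy in a study whose stated aim is diagnostic accuracy.

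**What to change.** In section 9.4:

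1. Define TP, TN, FP and FN as counts, with one set of abbreviations and with brackets in every ratio.
2. Delete sensitivity + (1 − specificity).
3. Define accuracy = (TP+TN)/(TP+TN+FP+FN).
4. List precision separately as PPV = TP/(TP+FP).
5. Have the authors attach the 0.5-to-1 sentence to the measure it describes: the AUC or, if a single summary of sensitivity and specificity was meant, balanced accuracy (sens + spec)/2. It should not be attached to plain accuracy, because an always-negative test scores 0.90 on accuracy at 10% prevalence and 0.70 at 30%.

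The cost is a wording change to the analysis plan. Recruitment, data collection and sample size are untouched.
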